10.7 Prior and Concomitant Medications

All medications will be coded using World Health Organisation (WHO) Drug Dictionary version B3 March 2020 or later.

Medications will be classified as prior or concomitant.

Prior medications are defined as any medication with an end date prior to first study vaccination (Day 0).

Concomitant medications are defined as any medication with a start or end date on or after date of first study vaccination.

10.8 Missing Data Values

All statistical analysis will be based on observed values. Apart from handling missing AE relatedness, missing values will neither be replaced, nor estimated.

10.9 Handling of Missing or Partial Dates

Missing or partial dates will only be imputed for the purpose of determining the timing of AEs or concomitant medications in relation to study vaccine dosing and for calculating the time since first diagnosis and duration of current anti-viral therapy.

Listings will present the original, reported dates.

10.9.1 Unsolicited AE Missing or Partial Dates

Unsolicited AEs will be considered treatment-emergent unless the partial start date indicates that the event began prior to first vaccination, i.e. if the month and/or year are before the month of first study vaccination.

For the purpose of determining if the unsolicited AEs falls within 28 days of each vaccination (vaccination date + 27 days), the following imputation of missing and partial start dates will be performed:

Missing day, month, and year

The day, month, and year of date of first vaccination will be assigned to the missing fields.

Missing day and month

If the year of the incomplete start date is the same as the year of the date of first vaccination, then the day and month of the date of first vaccination will be assigned to the missing fields.

If the year of the incomplete start date is before the year of the date of first vaccination, then December 31 will be assigned to the missing fields.

If the year of the incomplete start date is after the year of the date of first vaccination, then 01 January will be assigned to the missing fields.

Missing month only

The day will be treated as missing and both month and day will be replaced according to the above procedure.

Missing day only

If the month and year of the incomplete start date are the same as the month and year of the date of first vaccination, then the day of the date of first vaccination will be assigned to the missing day.

If either the year is before the year of the date of first vaccination or if both years are the same but the month is before the month of the date of first vaccination, then the last day of the month will be assigned to the missing day.

If either the year is after the year of the date of first vaccination or if both years are the same but the month is after the month of the date of first vaccination, then the first day of the month will be assigned to the missing day.

If the stop date is complete and the imputed start date is after the stop date, then the start date will be imputed using the stop date.

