#### *8.2.2 Study Reporting Period for Adverse Events*

The reporting period for all adverse events begins on the date the informed consent is signed. Solicited adverse events are recorded in the eDiary up to 7 days post-vaccination. All other events are recorded in the eCRF at all clinic visits throughout the study. All SAEs and/or AESIs are recorded until the final study visit and for all serious or study vaccine-related adverse events until these are resolved or until participant contact discontinues. Severe adverse events or SAEs that continue at the end of the study will be attempted to be followed until resolved or stabilised.

Adverse event information will be collected at study visits and participant will be instructed to call study team members to report any abnormalities during the intervals between study visits and to come to the study centre if medical evaluation is needed and the urgency of the situation permits.

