2.0 Change History

Version/Date	Change Log
1.0 16-Sep-2020	Created as new
1.1 19-Aug-2022	
Added partial AE imputation for determining if unsolicited AEs fall within 28 days of each vaccination
 
Changed the HBV DNA summary table from fold change from baseline to number and percentage of participants in each category
 
Removal of HBpgRNA and HBcrAg exploratory analyses
 
Addition of ICS and ELISpot definitions and analyses
 
Actual dose of nivolumab in mg/kg will be derived using baseline weight as weight is only collected at screening not at each visit
 
Added source of vital signs toxicity grading
 
Added visit windows for local/systemic reactogenicity
 
Updated list of laboratory parameters based on data received
 
Added list of DMC outputs to the appendix
 
Added laboratory toxicity grade appendix

1.2 09-Dec-2022	
Updated for Dry run 2 comments
 
Added HBsAg repeated measures analysis
 
Removed Kaplan-Meier analysis of HBeAg and HBsAg loss
 
Updated the seroconversion definitions
 
Added ICS and ELISpot analyses using non-parametric tests
 
Removed analyses for Month 3 boost (as no participants had the Month 3 boost)
 
Changed solicited AE analyses to combine the investigator (CRF) and eDiary data into a single analysis and removed the visit windowing for local/systemic reactogenicity
 
Added ALT and AST summary by time point

2.0 05-Jan-2023	
Up-versioned for signature
 
Updated ELISpot responder definition

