12.7.2 Other Safety Endpoints

12.7.2.1 Other Adverse Events

An overall summary of treatment-emergent adverse events, including the number of events reported, will be provided for:

- Any AEs
- Any AEs within 28 days of first vaccination
- Any AEs within 28 days of second vaccination
- Any grade 3 or greater AEs within 28 days of first vaccination
- Any grade 3 or greater AEs within 28 days of second vaccination
- Any AEs related to study vaccines
- Any AEs related to nivolumab

- Any AEs related to study vaccines or nivolumab
- Any grade 3 or greater AEs related to study vaccines
- Any grade 3 or greater AEs related to nivolumab
- Any grade 3 or greater AEs related to study vaccines or nivolumab
- Any AEs with outcome of death
- Any serious AEs
- Any serious AEs related to study vaccines
- Any serious AEs related to nivolumab
- Any serious AEs related to study vaccines or nivolumab
- Any AEs leading to discontinuation of study vaccines
- Any AEs leading to discontinuation of nivolumab
- Any AEs leading to discontinuation of study vaccines or nivolumab
- Any AEs of special interest

Deaths will be identified using the AE eCRF.

In addition, individual summary tables by SOC and PT will be provided for each category (with the exception of any AEs with outcome of death) in the overall TEAE table and presented similarly to the primary endpoint in Section 12.7.1.1. A by-participant summary of all TEAEs leading to death, serious TEAEs, and TEAEs leading to discontinuation of study vaccines or nivolumab will be produced.

AEs leading to discontinuation of study vaccines or nivolumab are defined as any AE with Action Taken with Study Vaccines = 'Drug Withdrawn' or Action Taken with Nivolumab = 'Permanently Discontinue' recorded on the Unsolicited AEs eCRF.

TEAEs will be further summarised by maximum severity (grade 1, grade 2, grade 3, grade 4, grade 5) within each SOC and PT. Participants with multiple events within a particular SOC or PT will be counted under the category of their most severe event within that SOC or PT.

Non-treatment-emergent AEs will be presented by SOC and PT.

All adverse events (including non-treatment-emergent events) recorded on the eCRF will be listed separately.

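### SAP 10.9.1 sets the treatment-emergent flag for incompletely dated AEs from the start date alone, so an event whose stop date precedes dose 1 is still counted as a TEAE

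*SAP*

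**What the plan says.** SAP 10.6 counts an event as treatment-emergent if it occurs during or after the first vaccine administration. Protocol 10.2.2.6 is to the same effect.

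For unsolicited AEs with incomplete start dates, SAP 10.9.1 gives a separate rule: "Unsolicited AEs will be considered treatment-emergent unless the partial start date indicates that the event began prior to first vaccination". It explains the exception as applying "if the month and/or year are before the month of first study vaccination". The stop date is not mentioned.

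The section then gives rules for imputing start dates, introduced with "For the purpose of determining if the unsolicited AEs falls within 28 days of each vaccination". The last of these is a stop-date check: "If the stop date is complete and the imputed start date is after the stop date, then the start date will be imputed" from the stop date. The SAP change history (Section 2.0, version 1.1) describes the addition in the same limited terms: "Added partial AE imputation for determining if unsolicited AEs fall within 28 days of each vaccination".

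Three other places matter:

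- Protocol 8.2.2: "The reporting period for all adverse events begins on the date the informed consent is signed". Protocol Section 6 allows a screening period of 42 days, so AEs that begin and end before dose 1 can be in the database.
- SAP 12.7.2.1 plans a table for them: "Non-treatment-emergent AEs will be presented by SOC and PT".
- SAP 12.7.1 lists the count and percentage of participants with TEAEs in each group as a primary endpoint.

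**The concern.** Counting an event as treatment-emergent when its timing is unknown is a reasonable, cautious default. Here the timing is not unknown. If the recorded stop date falls before dose 1, the event cannot have occurred during or after vaccination, however incomplete its start date is. As written, 10.9.1 still sends it to the TEAE tables and not to the non-treatment-emergent table.

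Two things are at stake. A primary safety endpoint would include events that the SAP's own definition excludes. And the SAP can treat one event in two ways: dated before vaccination for the 28-day tables, and counted as emerging after vaccination in the overall TEAE tables. Two programmers could reasonably code this differently.

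**Working it through.** No figure in the plan depends on this rule, so the check applies 10.9.1 literally to test events. The assumed first vaccination is 20 March 2021. The dose-1 window in SAP 10.9.1 and 12.7.1.1 is the vaccination day plus 27 days, so 20 March to 16 April.

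**Rules applied**

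1. Flag: treatment-emergent unless the known part of the start date (month and year, or year alone) is earlier than that of dose 1. A wholly missing start can never meet the exception.
2. Imputed start: the dose-1 date if the start is wholly missing, if only the year is known and matches, or if month and year match. If the month is earlier, the last day of that month.
3. Stop-date check: if the stop date is complete and earlier than the imputed start, the start becomes the stop date.

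**Results**

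| Case | Start recorded | Stop recorded | TEAE flag as written | Imputed start | In dose-1 window | TEAE flag if stop date is used |
|---|---|---|---|---|---|---|
| A | March 2021 | 5 March 2021 | Yes | 5 March | No | No |
| B | 2021 | 25 Feb 2021 | Yes | 25 Feb | No | No |
| C | missing | 25 Feb 2021 | Yes | 25 Feb | No | No |
| D | missing | Feb 2021 | Yes | 20 March | Yes | No |
| E | Feb 2021 | 10 March 2021 | No | 28 Feb | No | No |
| F | 5 March 2021 | 10 March 2021 | No (under 10.6) | not imputed | No | No |
| G | March 2021 | none | Yes | 20 March | Yes | Yes |

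In A to C the stop date is complete. The SAP's imputed start lies before vaccination while its flag says the event emerged afterwards, so the plan contradicts both 10.6 and its own imputed date.

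In D the stop date is partial, so the correction does not operate ("If the stop date is complete and the imputed start date is after the stop date" is its condition). The imputed start stays on the vaccination date. There is no clash between flag and imputed date, but the event enters the dose-1 28-day summaries as well as the TEAE tables, although February is wholly before dose 1.

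E and F are controls: already classified correctly, and unchanged by using the stop date. G has no informative stop date and properly stays treatment-emergent.

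**Effect of one misclassified participant**

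SAP 8.1 gives 10 and 9 participants for Groups 1 and 4, and 16 per group as the original plan. Protocol Version 6.0 keeps 16 as the target for Groups 2 and 3. If the participant has no other TEAE, the group percentage rises by 100/n:

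- n = 16: 100/16 = 6.25, or 6.3 points
- n = 10: 100/10 = 10.0 points
- n = 9: 100/9 = 11.1 points

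If the participant has any other TEAE, the participant count does not change; only the event counts do.

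**The case against.** The strongest reply is that the SAP should be read as a whole. Section 10.6 already excludes an event that ended before dose 1. The introduction to 10.9 says dates are imputed to place AEs in time relative to dosing, which is wider than the 28-day windows. On that reading the stop-date correction could govern the flag too. This does not carry the point. The flag has its own specific rule in 10.9.1, which names only the start date, and both the lead-in to the imputation rules and the change history confine them to the 28-day windows. A general introduction does not override that. At best, 10.6 and 10.9.1 conflict.

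Several practical replies do stand:

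- Incomplete dates should be uncommon. Protocol 7.4.1.2 collects start and end dates, 8.2.6.1 asks the investigator to estimate an uncertain resolution date, and 9.3 provides for checks and queries before lock. Case D in particular should be rare.
- The error over-counts TEAEs, which is the cautious direction for safety. The safety summaries are descriptive.
- With a complete stop date the 28-day summaries are already protected.
- Listings show the dates as reported (SAP 10.9), so a careful reader could find such an event.

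A reader might also infer that these events inflate the treatment-related tables. The documents do not support that in general. Protocol 8.2.4.2 makes timing a factor in the investigator's causality judgement, so an event that resolved before dosing would ordinarily be judged unrelated. It would reach those tables only if recorded as related, or if causality were missing and defaulted to related under SAP 10.5.2.

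**Conclusion.** The point holds as a narrow but definite error in a stated rule. It concerns unsolicited AEs that have a missing or partial start date not placed before the vaccination month, and a stop date that shows they ended before dose 1. These are counted as TEAEs contrary to SAP 10.6. With a complete stop date the flag also contradicts the SAP's own imputed start. With a wholly missing start and a stop known only to be in the month before dose 1, the event enters the dose-1 28-day summaries too.

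A reader might go further and infer that every screening-period event with an incomplete start date in the vaccination month, or with no start date, is misclassified. That is not so. Events without an informative stop date are truly ambiguous; the default to treatment-emergent is defensible for them, and the fix leaves them there.

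The documents give no rate of partial dates, so the number affected cannot be estimated; it is probably small. The shifts of 6.3, 10.0 and 11.1 points are per affected participant. They assume that the participant has no other TEAE and that the safety-set denominators equal the stated group sizes. The case for correction rests on a primary endpoint following its own definition at almost no cost, not on a large expected bias.

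**What to change.** Replace the first rule in SAP 10.9.1 with wording such as: an unsolicited AE with a missing or partial start date is treatment-emergent unless its start date, or its stop date (complete or partial), shows that it began or ended before first vaccination. For a partial stop date, this means a known month or year earlier than that of first vaccination.

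Add that any AE classified in this way as non-treatment-emergent is left out of the 28-day post-vaccination summaries. This deals with case D without having to assign a day to a partial stop date. AEs without an informative stop date stay treatment-emergent by default.

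The logic matches SAP 10.9.2, which already uses partial end dates to class a medication as prior.

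The cost is one sentence, with the consequent exclusion, and a small programming change. TEAE counts may fall slightly.

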## 6 STUDY PROCEDURES AT EACH VISIT/SCHEDULE OF ASSESSMENTS

The study consists of the following:

- A 42-day screening period before the start of study treatment
- A study period of 9 months
- An end of study visit

The schedule of assessments at each visit is shown in [Table 2](#) and listed in [Section 6.1](#) to [Section 6.3.1](#). The study assessments are described in [Section 7](#).

**Note: any additional visits or assessments performed during the study e.g. to assess adverse events must also be recorded on the unscheduled procedures or unscheduled visits in the eCRF.**

Unsolicited adverse events will be recorded from the date the informed consent is signed and at all clinic visits, by questioning the participant at each visit whether they had any adverse events since the previous visit and by observing the participant during clinic visits.

Serious adverse events and AESIs will be recorded from the date the informed consent is signed until the end of the study and/or resolved or until participant contact discontinues.

Solicited AEs and medication taken to treat solicited AEs will be collected daily in the eDiary for 7 days post-vaccination.

All medications taken to treat unsolicited AEs and SAEs will be recorded in the eCRF by questioning the participant at each visit whether they took any concomitant medications since the previous visit.

Due to the COVID-19 pandemic, study centres will follow any local procedures in line with testing to ensure the safety of participants and staff.

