**Table 2 Overall Schedule of Assessments at Each Study Visit**

Visit/Call	Screen	Vaccination Clinic	Telephone Call	Clinic	Vaccination Clinic	Telephone Call	Clinic			End of Study / Early Discontinuation Clinic
Timepoint (window)	Day						Month			
	-42 to -1	0	1 (+1d)	7 (±1d)	28 (+2d)	29 (+1d)	35 (±1d)	3 (±7d)	6 (±7d)	9 (±7d)
Informed consent	X									
Baseline/eligibility variables										
Demographics	X									
Inclusion and exclusion criteria	X									
Height and weight	X									
Medical and disease history	X									
HIV, HCV, HBV (quantitative HBV DNA and quantitative HBsAg), HDV serology	X									
Urinalysis	X									
Urine drug screen	X									
Urine pregnancy test (β-hCG)	X	X [a]			X [a]			X [f]	X [f]	X
Laboratory eligibility and safety tests										
Haematology	X	X [a]		X	X [a]		X	X	X	X
Biochemistry	X	X [a]		X	X [a]		X	X	X	X
Liver function tests	X	X [a]		X	X [a]		X	X	X	X
Study vaccination										
Vaccination dose		X			X			X [g]		
Post-dose observation		X			X			X [g]		
Nivolumab dose (Group 3 only) [b]					X					
Other safety assessments										
Full physical examination	X	X [a]			X [a]			X [a]		X
Symptom-directed physical examination				X			X	X	X	
Vital signs	X	X		X	X		X	X	X	X
Local/systemic reactogenicity		X [c]	X	X	X [c]	X	X	X [c]		
Unsolicited adverse events [d]	X	X	X	X	X	X	X	X	X	X
Serious adverse events and adverse events of special interest	X	X	X	X	X	X	X	X	X	X
Prior and concomitant medications	X	X	X	X	X	X	X	X	X	X
Blood for HBV disease markers [e]		X [a]		X	X [a]		X	X	X	X
Immunogenicity assessments										
Blood for cellular immunogenicity assessments		X [a]		X	X [a]		X	X [a]	X	X

[a] Pre-vaccination on Day 0, Day 28, and Month 3 (for UK participants having an MVA-HBV boost)

[b] Participants in Group 3 will receive nivolumab on Day 28. Group 4 is now closed. The patients will be observed for 30 minutes after vaccination. If there are no safety concerns (vital signs and reactogenicity), nivolumab will be infused over 30 minutes and the patients will be observed in the study centre for a further 30 minutes post-infusion.

[c] Captured pre-vaccination and post-vaccination on Days 0 and 28, and Month 3 (for UK participants having an MVA-HBV boost), via eDiaries for 7 days post-vaccination and then at the clinic assessment 7 days post-vaccination (Day 7 or 35)

[d] Recorded in the eCRF from the date the informed consent is signed, at all clinic visits to cover the period since the previous visit and during the visit

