##### *7.4.1.2 Unsolicited Adverse Events*

Unsolicited adverse events are other events meeting the criteria for adverse events (see [Section 8.2.1](#)) apart from those the participant is specifically asked about. Unsolicited adverse events, hospitalisations, other SAEs and AESIs will be collected for the duration of the study.

Participants will collect unsolicited adverse events in the eDiary and these will be reviewed during telephone calls with the participant and relevant information (event term, start and end date, severity, causality, outcome and seriousness) collected and entered into the eCRF as described in [Section 8.2.4](#).

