10.0 Conventions and Derivations

10.1 Treatment Groups

In the outputs, the treatment groups will be labelled as Group 1, Group 2, Group 3 and Group 4, rather than the full description of the first and second vaccinations, in order to conserve space. The definitions of these 4 groups are described in Table 1.

Table 1 Treatment Groups

Treatment Group	1 st Vaccination	2 nd Vaccination
Group 1	MVA-HBV 1 x 10 ⁸ pfu	MVA-HBV 1 x 10 ⁸ pfu
Group 2	ChAdOx1-HBV 2.5 x 10 ¹⁰ vp	MVA-HBV 1 x 10 ⁸ pfu
Group 3	ChAdOx1-HBV 2.5 x 10 ¹⁰ vp	MVA-HBV 1 x 10 ⁸ pfu + Nivolumab 0.3 mg/kg
Group 4	ChAdOx1-HBV 2.5 x 10 ¹⁰ vp + Nivolumab 0.3 mg/kg	MVA-HBV 1 x 10 ⁸ pfu + Nivolumab 0.3 mg/kg

For the safety analysis, the actual treatment groupings are assigned as follows:

- Group 1 = MVA-HBV in 1st vaccination
- Group 2 = ChAdOx1-HBV in 1st vaccination, No Nivolumab in 2nd vaccination
- Group 3 = ChAdOx1-HBV in 1st vaccination, Nivolumab in 2nd vaccination
- Group 4 = ChAdOx1-HBV + Nivolumab in 1st vaccination

The possible combinations of treatments at the first and second vaccinations and the resulting actual treatment group are described in Table 2.

Table 2 Actual Treatment Groups

Randomisation	Actual 1 st Vaccination Given	Actual 2 nd Vaccination Given	Treatment Group Assigned for the Safety Analysis
Group 1	MVA-HBV	MVA-HBV	Group 1
Group 2	ChAdOx1-HBV	MVA-HBV	Group 2

Randomisation	Actual 1 st Vaccination Given	Actual 2 nd Vaccination Given	Treatment Group Assigned for the Safety Analysis
Group 3	ChAdOx1-HBV	MVA-HBV + Nivolumab	Group 3
Group 4	ChAdOx1-HBV + Nivolumab	MVA-HBV + Nivolumab	Group 4
Group 1	MVA-HBV	No vaccination given	Group 1
Group 2	ChAdOx1-HBV	No vaccination given	Group 2
Group 3	ChAdOx1-HBV	No vaccination given	Group 2
Group 4	ChAdOx1-HBV + Nivolumab	MVA-HBV (Nivolumab not given)	Group 4
Group 4	ChAdOx1-HBV + Nivolumab	No vaccination given	Group 4
Group 3	ChAdOx1-HBV	MVA-HBV (Nivolumab not given)	Group 2
Group 4	ChAdOx1-HBV (Nivolumab not given)	MVA-HBV + Nivolumab	Group 3
Group 4	ChAdOx1-HBV (Nivolumab not given)	MVA-HBV (Nivolumab not given)	Group 2
Group 4	ChAdOx1-HBV (Nivolumab not given)	No vaccination given	Group 2

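### The partial-date rule for adverse events (AEs) ignores the second vaccination date, and Grade 3 or higher vaccine-related AEs within four weeks, a primary-endpoint component, have no described summary

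*SAP*

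**What the plan says.** SAP 10.9.1 gives the purpose of the imputation: to decide whether an unsolicited AE "falls within 28 days of each vaccination (vaccination date + 27 days"). The branches then run as follows.

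- **Start date fully missing:** set to the first vaccination date.
- **Day and month missing, same year as dose 1:** "the day and month of the date of first vaccination will be assigned to the missing fields".
- **Day missing, same month as dose 1:** set to the dose-1 date.
- **Day missing, month "after the month of the date of first vaccination, then the first day of the month will be assigned to the missing day"**.

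The second vaccination date appears in none of them. The only other date used is a complete stop date, when the imputed start would fall after it.

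SAP 12.7.1.1 reports AEs, SAEs and Grade 3 or higher AEs separately for the first and second 28-day windows. SAP 10.3 Table 3 allows dose 2 on Days 28 to 30.

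On the second matter, SAP 12.7.1 includes in the first primary endpoint Grade 3 or higher AEs that are vaccine-related and occur within four weeks of vaccination.

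**The concern.** The first two primary endpoints are counted in four-week windows, so a rule that moves events between windows acts directly on primary outputs. It matters most in Group 3, defined as "Group 3 = ChAdOx1-HBV in 1st vaccination, Nivolumab in 2nd vaccination": an event that followed nivolumab can be tabulated in a period before any nivolumab was given.

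The second gap is one of coverage. If no table meets all three conditions of a stated primary component, the plan as written does not report that component.

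**Working it through.** **Inputs.** Imputation rules from SAP 10.9.1. Each window is the vaccination date plus 27 days, that is 28 calendar days. Dose gap 28, 29 or 30 days (SAP 10.3 Table 3). The plan states no figure for partial dates, so there is none to reproduce.

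**Two examples** (dose gap 28 days, non-leap year)

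- *A.* Doses on 15 January and 12 February. The dose-1 window ends 15 January + 27 days = 11 February. An event dated only February becomes 1 February and counts under dose 1, even if it followed dose 2.
- *B.* Doses on 10 January and 7 February. The dose-2 window ends 7 February + 27 days = 6 March. A true onset of 25 March with the day missing becomes 1 March and counts under dose 2, although it lies outside both windows.

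**Enumeration.** Take 730 consecutive dose-1 dates and every onset day in a 28-day window: 730 × 28 = 20,440 cases per gap. Delete the day, apply the SAP rule, and classify the imputed date.

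| True onset, day missing | SAP places it | Gap 28 | Gap 29 | Gap 30 |
|---|---|---|---|---|
| Dose-2 window | Dose 1 | 52.3% | 49.1% | 45.8% |
| Dose-2 window | Dose 2 | 47.7% | 47.7% | 47.7% |
| Dose-2 window | Neither | 0% | 3.3% | 6.5% |
| Dose-1 window | Dose 1 | 100% | 100% | 100% |
| 28 days after dose-2 window | Dose 2 | 52.1% | 52.1% | 52.1% |

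The counts behind the first row are 10,696, 10,026 and 9,358 of 20,440. The last row is 10,646 of 20,440.

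**Net effect on each window's share of day-missing events**

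- *Onset uniform over Days 0 to 91.* The true share of each window is 28/92 = 30.4%. Under the SAP rule dose 1 takes 46.4%. That equals its upper bound, because every day-missing event that could lie in the dose-1 window is put there. Dose 2 stays at 30.4%, through offsetting errors: at gap 28, 15.9% is lost to dose 1 and 15.9% is gained from later onsets.
- *Onset uniform over Days 36 to 91.* The dose-2 share rises from 35.7% to 47.9% (gap 28) or from 39.3% to 48.8% (gap 30).

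**The missing component.** Compare the three conditions with the described summaries:

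| Summary | Grade 3 or higher | Vaccine-related | 28-day window |
|---|---|---|---|
| Primary component (12.7.1) | yes | yes | yes |
| 12.7.1.1 windowed tables | yes | no | yes |
| 12.7.2.1 windowed rows | yes | no | yes |
| 12.7.2.1 related row; Table 14.3.2.13 (16.0) | yes | yes | no |

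No row below the first meets all three conditions, and SAP 6.1 declares no change from the protocol on this point. Each partial summary is only an upper bound for the component, though a zero in either would make the component zero. Solicited AEs are all treated as related (10.5.5.1) and tabulated by severity after each dose (12.7.2.2), but for 7 days only.

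**The case against.** The strongest reply concerns weight.

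- Only the imputation step ignores dose 2; the imputed date is still compared with both windows. Taking the earliest possible on-treatment date is a recognisable conservative convention for dose 1. With onset uniform over Days 0 to 91, the net dose-2 bias is zero.
- Missing days may be rare. Start date is a collected item (Protocol 7.4.1.2), events are recorded in an eDiary and reviewed by telephone, and sites collect them "by questioning the participant at each visit whether they had any adverse events since the previous visit". A missing day is least plausible soon after dosing, where follow-up is closest.
- Other outputs are protected. The investigator judges relatedness to nivolumab separately, and missing relatedness counts as related (SAP 10.5.2). Nivolumab-related AEs and AEs of special interest are tabulated without a window, and "Listings will present the original, reported dates".
- For the missing component, the full output list is not visible: SAP 16.0 covers only the DMC and interim subset. The listings would also allow the count to be derived by hand.

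Most of this stands as a limit on size. It does not make the rule fit its stated purpose. The zero net bias depends on one onset pattern; in the Days 36 to 91 pattern dose 2 is over-counted. A stated primary component should not depend on hand derivation from listings.

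**Conclusion.** Both parts hold, and the SAP should be corrected. In the day-missing case, about half of true dose-2-window events are counted under dose 1 (45.8% to 52.3%), and 52.1% of events in the following 28 days are pulled into the dose-2 window. The dose-1 count can only be inflated; the net dose-2 error can go either way.

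These percentages are conditional on a missing day and assume uniform onset and dose dates spread over the calendar. The stop-date override was not applied. The number of partial dates is not given, so the absolute effect is unknown and may be small. Only unsolicited AEs with incomplete start dates are affected; the tables are descriptive, and whole-study AE, SAE and special-interest tables do not change. The gap in the primary component rests on the SAP text alone and needs no assumption about data.

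**What to change.** **SAP 10.9.1.** Use both vaccination dates.

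1. For each incomplete start date, find the range of dates it allows. Start the range no earlier than dose 1 for events treated as treatment-emergent, and end it no later than a complete stop date.
2. If the whole range lies in one window, assign the event there. If it overlaps a window but extends outside it, count the event in each window it overlaps and flag it as date-uncertain.
3. Report each window with and without flagged events, as upper and lower bounds.
4. Add a combined count for either window, with each event included once. Treat an event as certain there if its whole range lies within the two windows together.

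Example A is then flagged under both doses and certain in the combined count; Example B is flagged under dose 2. Imputing the dose-2 date instead would not do: it would move 46% to 52% of day-missing dose-1-window events to dose 2.

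**SAP 12.7.1.1.** Add Grade 3 or higher vaccine-related AEs within 28 days of the first and of the second vaccination, labelled as the primary-endpoint component.

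**Cost.** SAP wording, a programming change, two related Grade 3 or higher rows and one combined row. An uncertain event can appear under both doses, and the bounds can be wide:

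- With no stop date, only 0.3% of day-missing dose-2-window events are certain for dose 2. A complete stop date 2 days after onset raises this to 41.2%; 6 days after, to 29.8%.
- With onset uniform over Days 0 to 91, the dose-1 bounds are 14.5% to 46.4% and the dose-2 bounds 0.1% to 62.4%. The combined bounds are 44.9% to 76.9% at gap 28 and 14.6% to 79.0% at gap 30, where the windows no longer touch.

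These are shares of day-missing events; if few dates are partial, the reported bounds nearly coincide. If the eCRF holds the visit at which an event was first reported (not stated; an assumption), bounding the range by that visit and the one before narrows it further. About half of day-missing dose-2-window events then become certain. No event overlaps both windows, provided onsets on a visit day are dated.
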